9.2 Collection and Reporting of Adverse Events

It is the responsibility of the Investigator at the site to ensure that all adverse events (AEs, SAEs, ADEs, SADEs (ASADEs and USADEs) and device deficiencies) occurring during the course of the study are recorded on the Adverse Event Form. Details recorded should include the following information:

- A description of the event
- The dates of the onset and resolution
- Any action taken
- The outcome
- The relationship to the device
- Whether or not the adverse event is serious
- Whether the adverse events arises from insufficiencies in the IFU
- Whether the adverse event arises from user error

Any adverse events that occur during the course of the study should be treated by established standards of care that will protect the life and health of the study patients.

Adverse events can be observed directly by the site Investigator or staff, or can be spontaneously reported by the patient. In addition each patient should be questioned about adverse events at each study visit. In all cases it is the responsibility of the site Investigator to collect the information and record as outlined above. All adverse events should be followed up for the duration of the study.

In the case of SAEs, SADEs (ASADEs and USADEs) – including those resulting from device deficiencies), these must be reported to the study Sponsor and to the relevant Ethics Committee according to the term of approval and in addition, any local adverse event reporting guidelines should be followed.

Anticipated Adverse Events are as follows:

- Infection due to cross-contamination from other patient
- Irritation / erythema due to reaction to Disclosing Solution
- Hypersensitivity to the Disclosing Solution

- Pain or discomfort due to presence of intra-oral imaging device in mouth
- Damage/ trauma to soft tissue due to presence of intra-oral imaging device in mouth
- Choking hazard from patient biting down on Applicator

Serious Adverse Events, Serious Adverse Device Effects and Unanticipated Adverse Device Effects must be reported to the Sponsor, within 24 hours of becoming aware of the event. In addition a written report is to be provided by the Investigator within 5 working days.

SAEs, SADEs and UDAEs should be sent by email within the specified timelines to:

[contact] and [contact]

On receipt of any SAE, SADEs and UADEs, Calcivis Ltd will initiate a Safety Panel review within two working days of becoming aware of the adverse event, with Calcivis Management and Medical / Dental advisors, to determine if there is any safety requirement to stop the clinical study. Any such decision will be communicated to the Investigators as soon as reasonably possible.

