9. ADVERSE EVENTS

9.1 Definitions

Adverse Event (AE) – any untoward medical occurrence, unintended disease or injury, or untoward clinical signs (including abnormal laboratory findings) in subjects, users or other persons, whether or not related to the investigational medical device.

This definition includes events related to the investigational device and comparator and events related to the procedures involved.

For users or other persons, this definition is restricted to events related to the investigational medical devices.

A Serious Adverse Event (SAE) – is an adverse event that –

- Led to death
- Led to a serious deterioration in the health of a subject that –
 - resulted in a life-threatening illness or injury
 - resulted in a permanent impairment of a body structure or a body function
 - required in-patient hospitalization or prolongation of existing hospitalization
 - resulted in medical or surgical intervention to prevent a permanent impairment of a body structure or a body function
- Led to foetal distress, foetal death or a congenital abnormality or birth defect

Planned hospitalisation for a pre-existing condition, or a procedure required by the CIP, without serious deterioration in health, is not considered a serious adverse event

Adverse Device Effect (ADE) – an adverse event related to the use of an investigational medical device.

This definition includes any events resulting from insufficient or inadequate instructions for use, deployment, implantation, installation, or operation, or any malfunction of the investigational device.

This definition also includes any event resulting from user error or form intentional misuse of the investigational device.

Serious Adverse Device Effect (SADE) – adverse device effect that has resulted in any of the consequences characteristic of a serious adverse event.

Anticipated Serious Adverse Device Effect (ASADE) - an effect which by its nature, incidence, severity or outcome has been identified in the risk analysis report

Unanticipated Serious Adverse Device Effect (USADE) - serious adverse device effect which by its nature, incidence, severity or outcome has not been identified in the current version of the risk report.

Device Deficiency – inadequacy of a medical device with respect to its identity, quality, durability, reliability, safety or performance.

Device deficiencies include malfunctions, use errors and inadequate labelling.

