Device deficiencies which result in SADEs or USADEs, will be managed as detailed below.

Device deficiencies that did not lead to an adverse event, but could have led to a medical occurrence if suitable action had not been taken, or intervention had not been made or if circumstances had been less fortunate will also be managed as detailed below.

Use error – act or omission of an act that results in a different medical device response than intended by the manufacturer or expected by the user.

Use error includes slips, lapses and mistakes.

An unexpected physiological response of the subject does not itself constitute a use error.

Severity Definitions – the following definitions will be used to determine the severity rating for all SAEs

- Mild – awareness of signs or symptoms, that does not interfere with the subject's usual activity, or is transient which resolves without treatment and with no sequelae
- Moderate – a sign or symptom which interferes with the subject's usual activity
- Severe – incapacity with inability to do work or usual activities

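### A non-serious cross-contamination infection or hypersensitivity reaction to the Disclosing Solution has no deadline for reaching the sponsor and triggers no Safety Panel review (Protocol 9.1 and 9.2)

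*Protocol*

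**What the plan says.** Protocol 9.2 requires every adverse event to be entered on the Adverse Event Form, treated to usual standards and followed for the duration of the study. Its list of anticipated events includes "Infection due to cross-contamination from other patient" and "Hypersensitivity to the Disclosing Solution", with no limit on severity.

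Only some events carry a deadline: "Serious Adverse Events, Serious Adverse Device Effects and Unanticipated Adverse Device Effects must be reported to the Sponsor, within 24 hours" of awareness, with a written report within 5 working days. The panel rule uses the same classes: "On receipt of any SAE, SADEs and UADEs, Calcivis Ltd will initiate a Safety Panel review within two working days". The panel's stated task is "to determine if there is any safety requirement to stop the clinical study".

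Protocol 9.1 handles device deficiencies in two groups. The first is "Device deficiencies which result in SADEs or USADEs, will be managed as detailed below". The second is "Device deficiencies that did not lead to an adverse event, but could have led to a medical occurrence" had circumstances been less fortunate. Section 9.1 defines the unanticipated category for serious device effects only (USADE). The wider term used in 9.2, Unanticipated Adverse Device Effect (UADE), is not defined.

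**The concern.** Seriousness describes the harm to the patient who had the event. For these two events the question is also what it implies for the next patient. Protocol 6.1 counts applicator integrity, toxicity of the solution and vial contamination among its high-impact risks, and argues that an applicator breach would need three faults at once. Even a mild infection acquired from another patient would therefore suggest that several barriers had failed. A mild allergic reaction may say something about a solution lot.

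The sponsor keeps the master device accountability records (5.8), so it is the party best placed to act on a lot used at more than one site. Each site has one camera, and five Investigators work at four practices (7.2), so one camera serves two Investigators. Recruitment and procedures are expected to take only 2 to 3 months (7.3). A route with no deadline could therefore deliver the information after many of the patients have been imaged. Patients may be as young as 6, whereas the earlier study enrolled ages 16 to 25 (5.7).

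**Working it through.** The plan gives no figure to reproduce. The check is to follow one case through every route: a non-serious event that is on the anticipated list and is judged device-related.

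| Route | Condition | Met? |
|---|---|---|
| 24-hour report, serious classes (9.2) | SAE or SADE | No: not serious |
| 24-hour report, UADE, if the term includes non-serious effects | Not anticipated | No: on the list |
| 24-hour report, UADE, if the term means USADE | Serious and not anticipated | No: not serious |
| Report to sponsor and Ethics Committee (9.2) | SAE or SADE | No |
| Safety Panel (9.2) | SAE, SADE or UADE | No, for the same reasons |
| Deficiency causing harm (9.1) | Led to a SADE or USADE | No |
| Near-miss deficiency (9.1) | Led to no adverse event | No: an event occurred |
| Recording, treatment, follow-up (9.2) | Any adverse event | Yes, but no sponsor deadline and no panel |
| CRF completion (14.5), monitor contact and visits (14.4) | All patients | Yes, but no interval fixed |
| SAP 13.1 | All adverse events | Yes, as a listing at final analysis |

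The result is the same under either reading of UADE. On the 9.1 wording, a deficiency that hurts nobody has a stated route, while one that causes a mild infection has none.

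**Extra panel reviews under the fix.** Reviews = patients × event rate. Patients range from 85 to 180 (Synopsis). The rates of 0.1% and 1% are assumptions.

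- Lowest: 85 × 0.001 = 0.085
- Highest: 180 × 0.01 = 1.8

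**Earlier experience.** There were no infections or allergic reactions among 42 patients (5.7). The two-sided 95% upper limit is 1 − 0.025^(1/42) = 8.4%. This is reassuring but does not exclude rates well above those assumed.

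**Patients who might share a multi-use vial after Visit 2.** The inputs are 10 syringes per kit and 4 weeks of storage (5.9), Visit 2 at day 7 to 14 (8.3), and 17 to 36 patients per Investigator over 2 to 3 months. The pace r then runs from 17 / 13.04 weeks = 1.30 to 36 / 8.70 weeks = 4.14 per week. Assume that the vial is opened on the index patient's day, one syringe is used per patient, recruitment is even, and the Investigator takes no action. With Visit 2 at week t, the number still to share the vial is min(9 − r·t, r·(4 − t)), not below 0.

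- Maximum, at t = 1 and r = 2.25: 9 − 2.25 = 6.75 and 2.25 × 3 = 6.75
- Fastest single Investigator, t = 2: 9 − 4.14 × 2 = 0.7
- Two Investigators on one vial at 8.28 per week, t = 2: 9 − 16.56 is negative, so 0
- Two syringes per patient (4 others at most), r = 4.14, t = 1: 4 − 4.14 is negative, so 0
- If the infection came from an earlier patient on the same vial, at most 8 syringes remain: 8 − r = 3r gives r = 2 and a maximum of 6.0

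The range is roughly 0 to 7. These are possible exposures to one vial, not expected harms, and they apply only if the multi-use format is in use.

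**The case against.** The case against giving this much weight is good. Applicators are single-use and the camera is wiped between patients (5.5). The multi-use solution contains a preservative, the vial top is wiped with alcohol, syringes are single-use, and 6.1 rates the hazards as very unlikely. Sponsor representatives are available throughout Visit 1 (8.2), so the sponsor may well hear of an immediate reaction the same day. The monitor keeps regular contact (14.4). An event needing intervention to prevent permanent impairment is already serious under 9.1. The Investigator knows first, can set a camera or vial aside, and can obtain replacements (5.8). Since a camera belongs to one site, the sponsor's ability to link cases across sites helps mainly with a solution lot. The Instructions For Use, and the standard that 15.1 says the study follows (BS EN ISO 14155:2011), are not among the documents and may add steps.

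All of this lowers the likelihood and the weight. None of it sets a reporting time in the plan. The Visit 1 representatives provide technical support, and no such role is described for Visit 2, when a delayed infection could be found.

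A reader might infer that such events are merely written down. The documents do not support that, because treatment, follow-up and monitor checks are required. A reader might also infer that being on the anticipated list is what excludes them. That cannot be established while UADE is undefined, since non-seriousness alone may be the reason. Nor is it clear that infection from a contaminated vial always escapes: only infection from another patient is listed, so under the wider reading of UADE other vial infections may already be escalated.

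**Conclusion.** The gap holds as a reading of 9.1 and 9.2. For a non-serious case of either event, the plan sets no time for telling the sponsor and calls no panel, under both readings of UADE. A deficiency that causes a non-serious event falls between the two groups in 9.1. This is a low-weight but worthwhile improvement to patient safety.

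Two stronger inferences should be resisted. The figure of 0 to 7 patients sharing a vial is not a measure of benefit, because it assumes that the Investigator does nothing. The two-working-day rule is also not a time to action: it governs when the panel review starts, and decisions follow as soon as reasonably possible. With the present delay unknown as well, no before-and-after count of exposures can be supported. The conclusion is confined to the text of the plan.

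**What to change.** In Protocol 9.2, add that any suspected device-related infection, and any suspected allergic or hypersensitivity reaction to the Disclosing Solution, is reported to the sponsor within 24 hours whatever its seriousness or anticipated status. The report gives the lot number and, for the multi-use format, the date the vial was reconstituted. The existing Safety Panel reviews each such report, and its remit is widened to include withdrawing a lot, vial or camera. In 9.1, extend the device-deficiency text to deficiencies that caused a non-serious event. Local transient irritation, discomfort and gum abrasion stay on routine recording.

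The cost is a few sentences and a line in site training. The panel already exists, and SAP Listing 14 already has a device code and lot number field, so only the reconstitution date is new. The downside is an occasional panel review of a mild event. The estimate of 0.1 to 1.8 covers infection and allergy only and does not count work arising from the 9.1 extension. Redefining UADE to take in all unlisted non-serious effects is not needed for this fix and could add reviews that have not been costed.

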10. STATISTICAL ANALYSIS

10.1 Sample size

The study will assess the agreement between the Calcivis System and dentist rating of suitable teeth in two teeth populations: 'no visible lesions', and 'active lesions'. Based on previous study data and expert opinion, 'No visible lesions' are expected to correspond to 'no luminescence' according to the Calcivis system in at least 70% of cases. Similarly, 'active lesions' are also expected to correspond to 'luminescence' in at least 70% of cases.

Subjects will provide no more than one tooth of each tooth population. The study sample size is calculated in terms of the number of teeth of each tooth population required. The number of subjects required is then *at most* the total number of teeth required.

For the purpose of sample size calculations, the percentage agreement for each of the two tooth populations are jointly considered as measures of agreement. That is, the study will be deemed a success if the percentage agreement in both of the tooth status populations is statistically significant at the 2.5% level when compared to chance agreement (50%).

Expressed in terms of hypothesis tests, the null and alternative hypotheses are:

$$H_0: p_{a,i}=0.5 \text{ vs. } H_1: p_{a,i}>0.5 \text{ for each tooth status population } i$$

where $p_{a,i}$ is the percentage agreement in tooth status population i .

To achieve at least 90% power overall, a power of 94.9% has been used for each tooth status population individually. The planned method of analysis is an exact binomial test and this has been used to derive a required sample size of 81 for each of the tooth status populations. This is the first sample size after which all subsequent sample sizes provide at least 94.9% power.

10.2 Statistical Analysis

General Considerations

The planned statistical analysis will be fully described in a Statistical Analysis Plan, which will be finalised prior to the locking of the study database. The main details of the planned analysis are described below.

The statistical analysis will be performed using SAS version 9.2 or higher.

All statistical tests will be conducted one-sided with a 2.5% level of significance and no adjustment will be made for multiple testing.

Analysis Populations

All patients on whom the Calcivis System is used will be included in the Safety Population.

The Agreement Population will include all teeth on which there is a dentist ICDAS score.

Analysis

The percentage agreement of the original dentist ICDAS score and the independent reviewer Calcivis finding ('no luminescence' or 'luminescence') will be presented along with an exact one-sided 97.5% confidence interval and p-value comparing the percentage agreement to 0.5 for the following:

- Teeth rated with 'no visible lesion' that are assessed as 'no luminescence' by the Calcivis System;
- Teeth rated with an 'active lesion' that are assessed as 'luminescence' by the Calcivis System.

The analysis of agreement will be performed on the Agreement Population.

The agreement between the original dentist ICDAS score and Calcivis finding will be analysed in the same manner.

User and patient questionnaire data and adverse events will be summarised descriptively for the Safety Population.

Missing Data

Missing data arising from teeth where the Calcivis System assessment is uninterpretable for reasons that are thought unrelated to the assessment outcome, will not be imputed. The reasons will be pre-defined in the Statistical Analysis Plan. Otherwise missing data will be considered as a disagreement in the calculation of agreement. Secondary analyses based on imputing all missing data as a disagreement will be conducted, if appropriate.

Otherwise missing data will not be imputed.

Interim Analysis

No interim analysis is planned for this study.

11. DATA MANAGEMENT

All data collected on the Case Report Forms will be 100% verified against source data (Patient's Dental / Medical Records and Source Document Worksheets) by the monitoring staff. The data from the CRFs will be entered on to a validated Database. Quality control of the data entry process will be performed and any resulting discrepancies adjudicated against the CRFs. The data will then be subjected to validation checks and any resulting Data Queries will be resolved at site with the assistance of the monitoring staff. Once all Data Queries are resolved, critical data will be 100% verified (including adverse events), comparing the Database against the CRF.

The database will then be locked and the study data prepared for statistical analysis.

Any data existing for patients who withdraw voluntarily or are withdrawn from the study, will be used in the study analysis, unless the patient states this is contrary to their wishes.

Details of the data to be presented will be outlined in the Statistical Analysis Plan.

12. STUDY DATA REPORTING AND STUDY REPORT

A final Clinical Study Report of the results will be compiled by Calcivis Ltd which will be approved and signed off by each participating Investigator. A copy will be made available to each Investigator. In addition, a lay summary report of the clinical study results will be produced and made available for any patients who request a copy.

Copies of the final Clinical Study Report will be provided to the Research Ethics Committee, NHS R & D and any other local approvers.

13. PUBLICATION OF RESULTS

Calcivis Ltd commits to communicating or otherwise making available for public disclosure the results of the study regardless of the outcome. Public disclosure includes publication of a paper in a scientific journal, abstract submission with a poster or oral presentation at a scientific meeting, or by other means.

At the end of the study, one or more manuscripts for publication will be prepared in collaboration between the all Investigator(s) and Calcivis Ltd on the collective study results. Calcivis Ltd will not suppress or veto publications, however Calcivis Ltd reserves the right to postpone publication and / or communication for 180 days to protect intellectual property.

Any subsequent publications, (journal submissions, posters, white papers, marketing literature etc.) will be covered in a separate Publication Strategy document provided by Calcivis Ltd.

Calcivis Ltd will register this clinical study on www.clinicaltrials.gov website and report the study results accordingly.

14. REGULATORY, ADMINISTRATIVE AND CONTRACTUAL INFORMATION

14.1 Sponsor's Responsibilities

The Sponsor, (Calcivis Ltd) is responsible for providing Investigators with the information and training they need to conduct the clinical study properly and in accordance with the Clinical Study Plan. The Sponsor must ensure proper monitoring of the Clinical Study, that Research Ethics Committee approval, NHS, R & D approval and any other required local approvals are obtained and remain current, and that the Research Ethics Committee, NHS, R & D and other local approvers are informed of significant new information about the clinical study as required.

This information should include the following:

- A current signed copy of the Clinical Study Plan and any amendments
- A signed copy of the signed Clinical Investigation Agreement or equivalent Contract - for each participating Investigator / Site
- All information pertaining to Research Ethics Committee review and approval of this clinical study including a copy of the REC Letter of Favourable Opinion and a blank copy of the approved Patient Information / Consent Form for all sites involved.
- All information pertaining to NHS, R & D or other local approvals / notifications of this clinical study including a copy of the approval letter for each site.
- Copies of current signed and dated Curriculum Vitae's of the Investigator and all relevant site personnel

14.2 Amendments

Any change or addition to this Clinical Study Plan requires a written amendment which must be approved by the Sponsor before the change or addition can be considered effective. Where Research Ethics Committee approval is required, the Principal Investigator must submit the appropriate documentation to the main Research Ethics Committee, and obtain written approval for the amendment before it can be implemented at the investigative site(s). A copy of the written approval must be provided to the Sponsor. All Investigators must submit relevant documentation to each site's NHS, R & D or other relevant local approver and obtain approval before the Amendment can be implemented. Copies of the written approvals must be submitted to the Sponsor. Amendments will be circulated promptly to all investigators by the Sponsor.

